**STUDY INTERVENTION(S) / INVESTIGATIONAL AGENT(S):**

Image guided injection of the sciatic nerves with 2% lidocaine, 10 mL

vs.

Image guided injection of the sciatic nerves with preservative-free saline, 10 mL

IND exemption criteria for 2% lidocaine:

[figure not shown]
- The drug is lawfully marketed in the United States: Yes, 2% lidocaine is used as a standard local anesthetic in many medical offices throughout the United States.
- The research is not intended to be reported to the FDA as a well-controlled study in support of a new indication for use nor intended to be used to support any other significant change in the labeling for the drug: Correct, our study is not evaluating the efficacy of lidocaine. Rather, it is evaluating a procedural technique that requires analgesia. Analgesia is well established property of 2% lidocaine.
- The research is not intended to support a significant change in the advertising for the product: Correct. Lidocaine will be used to deliver analgesia. This is not a novel application of this medication.
- The research does not involve a route of administration or dosage level or use in a patient population or other factor that significantly increases the risks (or decreases the acceptability of the risks) associated with the use of the drug product: Correct, we will be using a volume and concentration that is well within standard sodium channel blocker safety limits. Furthermore, we will use ultrasound guidance to deliver the medicine and effectively avoid intravascular administration of the medication, further reducing its risk.
- The research is conducted in compliance with the marketing limitation described in 21 CFR §312.7: Correct, we will not be promoting an investigational new drug in this study. Rather, we will be using a drug with well-established analgesic properties in a novel procedural technique.

**PROCEDURES INVOLVED:**

Study Design

We aim to conduct a single-site, prospective, randomized, triple blind, sham-controlled, cross-over trial of consecutive participants to determine the efficacy of contralateral sciatic nerve block in treating chronic, refractory PLP/RLP.

**Figure 1: Study Crossover Design**

## Methods

Twenty participants will be recruited from the Northwestern-affiliated practices of the PI and the Co-I, the Shirley Ryan Ability Lab, the University of Chicago, and local prosthetic clinics.

*Pre-visit:* Candidates will be screened by authorized research personnel via chart review to determine candidacy for the study. If the participant meets eligibility criteria, they will be scheduled for a clinic visit.

### *Visit 1 – Consent, inclusion screening, and prosthetic step counter placement*

All participants will present to the Pain Clinic ([name]) and undergo an informed consent process with authorized research personnel. Eligibility criteria will be reviewed and confirmed. [name] will meet with the participant, explain the treatment block procedure, will review the medical history and perform a brief physical examination (focusing on residual limb point of maximal tenderness, review of prior imaging studies if available, and lower extremity musculoskeletal examination). Participants will provide baseline outcome measures and demographic data. Participants will be asked to complete the OPUS and GARS survey and provide demographic information. They will be given the option of completing these either on paper or on an iPad.

### *Devices*

During initial evaluation (visit 1), participants' prostheses will be fit with a Modus StepWatch™ or Evolution EvoWalk™. This will be tested in clinic by a research coordinator to ensure proper step count. The device will remain on participant's prosthesis until study completion. Participant kinematic and gait data will be recorded by Modus StepWatch™ or Evolution EvoWalk™ and uploaded via Bluetooth to secure a de-identified, Health Insurance Portability and Accountability Act (HIPAA) compliant cloud-based storage application and extracted by research coordinator to an encrypted, HIPAA-compliant, Northwestern research database (REDCap).

Participants will also be instructed to maintain a daily pain log through My Pain Diary smartphone application or paper log depending on participant preference. They will be asked to log daily pain scores during their treatment. Data will be extracted by a researcher to an encrypted, HIPAA-compliant, Northwestern research database (REDCap).

### *Visit 2 (procedure 1)– Randomization and Study Intervention*

STU#:

Eligible participants will return to the Lavin 14th floor Pain clinic within 2 weeks of the initial visit. Participants will be randomized to treatment or sham group. Participant pre-procedure 1 NRS pain score will be collected. Individual pain log will start 15 minutes after procedure. Participant will log pain score every hour until asleep. The next day, participant will record daily NRS pain score for 5 days.

Randomization

A computer-generated 1:1 block randomization scheme (<https://www.randomizer.org>) will be used to assign participants to receive a peri-sciatic nerve injection with either 10 mL of 2% lidocaine or 10 mL of preservative-free saline (compounded by the 11th floor Lavin pharmacy and labeled with a “1” or “2” to ensure adequate blinding). Randomization will be performed by a research assistant by opening an opaque envelope to reveal the participant number and group assignment printed inside of the envelope. This will instruct authorized study personnel to draw up either 2% lidocaine or saline (labeled “1” or “2” by compounding pharmacy per above). The blinded injectionist will be provided an unlabeled syringe of injectate immediately before the injection procedure. Participants, injectionist, and study personnel who collect outcomes data will be blinded to group assignment.

Treatment block of sciatic nerve in contralateral limb: Procedure planning will be based on the participant’s indication of residual limb point of maximal pain (measured by distance from posterior superior iliac spine (PSIS) to most painful point [in cm]). Note that this point may beyond the anatomic end of the residual limb. The block will be performed at the exact same distance from PSIS on the contralateral side. If the block cannot be performed at this site due to anatomic or technical considerations (such as proximity to vascular structures), a more cephalad site along the sciatic nerve course will be selected for the procedure. During the block procedure, the participant will be positioned prone. Standard American Society of Anesthesiologists (ASA) procedure monitoring will be used (pulse oximetry, ECG, blood pressure, and heart rate). The participant’s skin will be prepared with chlorhexidine. A sterile ultrasound probe will be placed on the participants’ residual limb at a transverse angle in order to view the nerve in short-axis. The skin will be anesthetized with 1-2 mL of 1.0% lidocaine. The ultrasound probe (in plane) will be advanced to the intact limb’s sciatic nerve equidistance to that of the residual limb point of maximal pain. A 22-gauge standard echogenic needle will be placed adjacent to the sciatic nerve with ultrasound guidance. At the site of the nerve, 10mL of 2% lidocaine will be injected through the needle in the intervention group and 10ml of saline will be injected in the sham group.

In treatment group: At the site of the nerve, 10mL of 2% lidocaine will be injected through the needle

In control group: At the site of the nerve, 10ml of saline will be injected through the needle

Following injection, participants will be kept in recovery area and monitored for 30 minutes. They will also complete a pain log starting 15 minutes post-injection. After the first pain score is recorded, the participants will dress and exit procedure area. Participants will be required to arrange transportation as the block may impair lower extremity motor function.

Both saline and local anesthetic will be administered to all subjects with a crossover design as described above. Participants will undergo 5-day washout between injections.

*Visit 3 – Crossover for both groups*

Eligible participants will return to the Lavin 14th floor Pain clinic within 5 days of visit 2. Participant pre-procedure 2 NRS and OPUS will be collected. Note that this will serve as post-procedure 1 washout and pre-procedure 2 intervention data point.

Both groups: will cross over and undergo treatment as described in *Visit 2*. Participant pain log will start 15 minutes after procedure 2. Participant will log pain scores every hour until asleep. The next day, participant will record daily NRS pain score for 5 days.

*Telephone call 1,2,3:* participant will be called at 1- and 5-days post-procedures for NRS, OPUS survey and safety monitoring by research coordinator (see Safety Monitoring below).

**SAFETY MONITORING** Participants will be contacted one day following both interventions to assess for any adverse events or side effects.

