## STUDY TIMELINES

- IRB submission and approval process: 2 months
- Recruitment: 12 months
- Statistical analysis and manuscript: 2 months
- Duration of participation for each participant is approximately: 3 weeks

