## **PROVISIONS TO MONITOR THE DATA TO ENSURE THE SAFETY OF PARTICIPANTS**

A data safety monitoring board consisting of the Department of Anesthesiology Director of Research, a pain medicine attending physician, a statistician, and study research personnel will periodically evaluate the data collected to determine whether participants remain safe. Safety data and adverse event data will be reviewed using the medical record and data collection form. It will be reviewed every 10 subjects or if one of the study subjects experiences a rapid response team intervention. Data will be compared between groups using the  $\chi^2$  statistic or the Fisher's exact test. A p-value  $< 0.05$  will be required to reject the null hypothesis.

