### **QUALIFICATIONS TO CONDUCT RESEARCH AND RESOURCES AVAILABLE**

There is a large volume of chronic pain patients treated annually at NMH, ensuring the participant sample projections can be achieved. In addition, a co-investigator serve as faculty at the Shirley Ryan AbilityLab, the nation's largest amputee rehabilitation program. The principal investigator has 22 years of clinical experience performing ultrasound-guided nerve blocks in both a clinical and research setting. He has authored several peer reviewed articles on the topic of perineural injections for pain indications.

All research team members have completed the necessary regulatory training. We anticipate 1-2 cases per week. Authorized research personnel will have dedicated time to recruit participants. All authorized research personnel are informed about the protocol and their duties and functions.

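### A fall at home after a block that may weaken the intact leg does not bring safety review forward, and no assistance is stated for leaving the procedure area

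*Combined protocol and SAP*

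**What the plan says.** All text on the procedure is in the combined protocol and SAP, under Visit 2 (procedure 1).

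- **Which leg.** The injection goes to the sciatic nerve of the intact limb: "The block will be performed at the exact same distance from PSIS on the contralateral side".
- **The hazard and the measure for it.** "Participants will be required to arrange transportation as the block may impair lower extremity motor function". No other measure is linked to loss of motor function.
- **Recovery.** "Following injection, participants will be kept in recovery area and monitored for 30 minutes". What is watched in that half hour is not stated. The one list of monitored items belongs to the procedure itself: "Standard American Society of Anesthesiologists (ASA) procedure monitoring will be used (pulse oximetry, ECG, blood pressure, and heart rate".
- **Leaving.** The pain log starts at 15 minutes. Once that first score is recorded, participants dress and leave the procedure area. No escort, wheelchair, walking aid or advice on walking is mentioned.
- **Follow-up.** Under Safety Monitoring: "Participants will be contacted one day following both interventions to assess for any adverse events or side effects". The Visit 3 section adds that the calls at 1 and 5 days include safety monitoring.
- **Review of safety data.** The section on monitoring data for participant safety describes a board and sets its timing: "It will be reviewed every 10 subjects or if one of the study subjects experiences a rapid response team intervention". Groups are compared by chi-square or Fisher's exact test at p < 0.05. The Study Summary, however, answers No to having a DSMB, DMC or IDMC.

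**The concern.** For an amputee, the injected leg is the one relied on most. After the lidocaine injection a participant may be standing on a prosthesis and a partly blocked leg. The harm to expect is a fall, most likely after leaving the clinic.

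The only event that brings board review forward is a rapid response team intervention, and a fall at home would not ordinarily lead to one. The rule therefore misses the setting in which the acknowledged hazard would mostly show itself. At stake are the safety of subjects still to be treated and the value of the complications outcome (secondary outcome 7). The primary efficacy comparison is not in question.

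**Working it through.** The plan derives no figure on this point. Its N = 20 is taken as given; an exact two-sided McNemar calculation on the stated inputs needs 18 pairs (power 0.83), and 18/0.90 = 20.

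**Step 1. Match the hazard to the measures.**

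- Motor impairment of the intact leg: recognised.
- Journey home: covered by arranged transport.
- Standing and walking before and after the journey: no stated measure.
- Detection: the day-1 contact would probably pick up a fall.
- Escalation: a fall or serious adverse event reported on that call meets neither review condition.

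**Step 2. Subjects treated before the next required review.** Inputs: 20 subjects, and a review after each 10. Assume that subjects are treated one after another and that the count is of treated subjects. If the fall is in subject k of a block of 10, then 10 − k further subjects are treated first.

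- Maximum (k = 1): 10 − 1 = 9.
- Minimum (k = 10): 0.
- Mean, if every position is equally likely: (9 + 8 + … + 0)/10 = 45/10 = 4.5.

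Scheduled reviews fall after subjects 10 and 20. Only the first comes while anyone remains to be treated. After a fall in any of subjects 11 to 19, all remaining subjects would be treated before the board had to look.

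**Step 3. The longest wait in calendar time.** The documents give two paces: "We anticipate 1-2 cases per week" in the section on qualifications and resources, and "Recruitment: 12 months" in the study timelines.

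- A case is a participant: 9/2 = 4.5 weeks to 9/1 = 9 weeks.
- A case is one injection: 9 × 2 = 18 injections, so 18/2 = 9 weeks to 18/1 = 18 weeks.
- 20 subjects over 12 months: 9/(20/52) = 23.4 weeks.

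**Step 4. Would the planned test pick up falls at a scheduled review?** Take the most favourable case, with every fall after lidocaine and none after saline, and treat the injections as independent groups. Two-sided Fisher p-values:

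| Falls, lidocaine vs saline | 10 vs 10 injections | 20 vs 20 injections |
|---|---|---|
| 3 vs 0 | 0.211 | 0.231 |
| 4 vs 0 | 0.087 | 0.106 |
| 5 vs 0 | 0.033 | 0.047 |

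Five falls against none are needed to reach p < 0.05 at either review. A trigger for falls therefore has to rest on clinical judgement of the event and not on significance.

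**The case against.** The strongest reply is that a protocol's silence is not evidence of what the clinic does. This limits several readings that a reader might otherwise infer.

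- **That participants are sent home unchecked.** Not supported. The content of the 30-minute monitoring is left open, the vital-signs list applies to the procedure, and an existing clinic discharge routine may include a strength check. What stands is that the protocol neither states nor cites one.
- **That discharge is at 15 or 30 minutes.** Not supported. Leaving the procedure area is not said to be leaving the clinic, and 30 minutes is a monitoring period. Any figure for weakness remaining at discharge would need an assumed discharge time and an assumed block duration, so none is given here.
- **That a fall would go unnoticed or unanswered.** Not supported. There are calls at days 1 and 5, complications are an outcome, and nothing stops staff acting at once. The gap is only that early review is not required.
- **That falls are likely.** The documents give no fall risk. A probability worked from an assumed risk would mostly restate the assumption.
- **That participants are not warned.** The lists under Risks to Participants do not name leg weakness or falls, but the consent pages are not available and the Visit 2 text itself names motor impairment. At most this is missing detail.

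Two further objections bear on the delay figures. They depend on a board that the Study Summary says does not exist. The review rule also does not say whether subjects are counted when enrolled, treated or completed, and participants with two injections some days apart may overlap. The count of 9 therefore holds only for strictly sequential treatment.

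**Conclusion.** The point holds in a limited form. The review rule does not cover a fall or serious adverse event at home, although the plan itself names the motor effect that could cause a fall. No help is stated for leaving the procedure area on a possibly weak intact leg. Under sequential treatment, 0 to 9 further subjects (mean 4.5) may be treated before review is required. The longest wait lasts 4.5 to 23.4 weeks, depending on which stated pace applies and what a case means. One of the two scheduled reviews comes too late to protect anyone.

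This is a worthwhile safety improvement at low cost. It is not a finding that the trial is unsafe. A reader might also infer that the primary result is compromised. The documents give no ground for that, and no such effect is claimed.

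**What to change.** 1. **Review trigger.** In the section on monitoring data for participant safety, add any serious adverse event, and any fall within 24 hours of an injection, as a trigger for prompt clinical review that does not depend on p < 0.05. Correct the Study Summary so that it agrees that a board exists.
2. **Exit.** In the Visit 2 procedure text, keep every participant for the full 30 minutes. Then, identically after both injections and regardless of any strength finding, have them leave by wheelchair or with an escort. Advise no unaided walking for a fixed number of hours set by the investigator.
3. **Day-1 call.** On the existing call, ask about falls after the NRS and OPUS have been recorded.

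A pass/fail strength check, with a longer stay or wheelchair only for those who fail, is a tempting alternative but a poorer one. Failures would occur mainly after lidocaine. They could cue allocation before the 1 to 6 hour scores and, through memory of the first visit, before the period-2 primary score. One rule for everyone avoids that added cue.

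The cost is an occasional extra review, a little existing staff time and some protocol wording. The walking advice may also lower first-day step counts after both injections, which touches the 24-hour point of secondary outcome 2.

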### Secondary Outcomes (between and within-group comparisons will be used for each outcome):

- 1) Mean and standard deviation (SD) of change in NRS pain score at 1, 2, 3, 4, 5, 6, 24, 48, 72, 96, 120 hours post-saline and lidocaine injections
- 2) Mean and SD of average daily steps recorded at 24, 48, 72, 96, 120 hours post-saline and lidocaine injections (via Modus StepWatchTM or Evolution EvoWalkTM)

STU#:

- 3) Mean and SD of change in Orthotics and Prosthetics User's Survey (OPUS) score immediately post-injection and conclusion of washout (5 days) in saline and lidocaine groups
- 4) Mean and SD of change in Groningen Activity Restriction Scale (GARS) score immediately post-injection and conclusion of washout (5 days) in saline and lidocaine groups
- 5) General linear model analysis of the interaction between crossover sequence
- 6) Demographic factors associated with large improvement in NRS pain score
- 7) Complications associated with the procedures

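### The Visit 3 timing has a latest limit but no earliest one; it fits the 5-day washout and the 120-hour outcomes only at exactly day 5, and no rule cuts off first-period data at procedure 2

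*Combined protocol and SAP*

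**What the plan says.** All references are to the combined protocol and SAP.

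- **Visit 3 timing** (Visit 3 – Crossover for both groups): "Eligible participants will return to the Lavin 14th floor Pain clinic within 5 days of visit 2".
- **Washout** (end of the treatment-block text under Visit 2): "Participants will undergo 5-day washout between injections".
- **Step outcome** (Secondary Outcomes, item 2): "Mean and SD of average daily steps recorded at 24, 48, 72, 96, 120 hours post-saline and lidocaine injections".
- **Other secondary outcomes**: item 1 sets change in NRS at hours 1 to 6 and then at 24, 48, 72, 96 and 120 hours after each injection. Items 3 and 4 set OPUS and GARS right after injection and at the end of washout, which they equate with five days.
- **Diary** (Visit 2): hourly scores on the day of injection, then five daily scores from the next day. After the second injection the log restarts: "Participant pain log will start 15 minutes after procedure 2".
- **Collected at Visit 3**: "Participant pre-procedure 2 NRS and OPUS will be collected". On its role: "Note that this will serve as post-procedure 1 washout and pre-procedure 2 intervention data point".
- **Calls** (numbered 1, 2 and 3): "participant will be called at 1- and 5-days post-procedures for NRS, OPUS survey and safety monitoring by research coordinator".
- **Step counter** (Devices): it stays on the prosthesis until the study ends.
- **Statistical Plan**: no rule assigns step or diary values to a treatment period.

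**The concern.** The visit sentence gives an upper bound on the gap between injections, whereas the washout sentence and the five-day outcomes need a lower bound of the same length. The only gap that meets both is exactly five days, and no tolerance is given. The sentence cannot simply be assumed to mean a visit on day 5: Visit 2 is timed relative to Visit 1 with the same construction, and there it plainly sets a latest date.

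If a participant attends early, the two periods run into each other. One diary day becomes both a late point after the first injection and an early point after the second. Steps taken after the second injection can be credited to the first. The reading meant to mark the end of a five-day washout is taken before five days have passed.

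In a crossover this mixes lidocaine and saline data within a participant, and values recorded after the second injection cannot be repaired later. At stake are the late secondary outcomes: NRS and steps up to 120 hours, and five-day OPUS and GARS.

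**Working it through.** **1. The plan's own figures that might settle the interval.**

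*Duration.* Study Timelines gives about 3 weeks per participant. With Visit 2 at its latest (14 days after Visit 1), Visit 3 after 1 to 5 days and 5 days of follow-up:

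14 + 1 + 5 = 20 days (2.9 weeks) up to 14 + 5 + 5 = 24 days (3.4 weeks).

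Both ends are about 3 weeks, so this figure does not separate an early visit from a day-5 visit.

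*Calls.* Two call days × two procedures = 4, but three are numbered.

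- Visit 3 on day 5: the visit replaces one call, leaving calls on days 1, 6 and 10, which is three.
- Visit 3 on day 4: the day-5 call after procedure 1 is also the day-1 call after procedure 2, giving days 1, 5 and 9, which is again three.

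The count fits day 5 but does not prove it.

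**2. The permitted gap.** Let T be the hours from procedure 1 to procedure 2.

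- Visit 3 sentence: T ≤ 120.
- Washout and 120-hour or five-day outcomes: T ≥ 120.
- Both together: T = 120, a window of zero width. Taken in hours, T = 115 falls short of the washout and T = 124 exceeds the visit limit.

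**3. First-period points falling after procedure 2.** The daily points are 24, 48, 72, 96 and 120 h (5 step points). NRS adds hours 1 to 6, making 6 + 5 = 11. Count the points later than T:

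| Visit 3 at | Points after procedure 2 | Share of 5 step points | Share of 11 NRS points | Protected NRS/OPUS reading taken at about |
|---|---|---|---|---|
| Day 5 (120 h) | 0 | 0% | 0% | 120 h |
| Day 4 (96 h) | 1 | 1/5 = 20% | 1/11 = 9.1% | 96 h |
| Day 3 (72 h) | 2 | 2/5 = 40% | 2/11 = 18.2% | 72 h |
| Day 2 (48 h) | 3 | 3/5 = 60% | 3/11 = 27.3% | 48 h |
| Day 1 (24 h) | 4 | 4/5 = 80% | 4/11 = 36.4% | 24 h |

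Overlap examples: on day 4, the 120-h point of period 1 is the 24-h point of period 2. On day 3, 96 h coincides with 24 h and 120 h with 48 h.

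**4. What remains on day 5 itself.** The NRS and OPUS readings before procedure 2 can stand for the end of period 1, even if taken a few hours short of 120 h. Steps are different: each hour by which procedure 2 is earlier in the day than procedure 1 was puts 1/24 = 4.2% of the 96–120 h window after the second injection.

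**5. GARS.** It is due at five days under item 4. It is named at Visit 1 and, without a time, in the Data list. Visit 3 and the calls name only NRS and OPUS, so no listed contact collects it at the end of washout.

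**The case against.** The strongest reply is that the washout sentence, which comes just before the Visit 3 heading, is itself a minimum interval. Read with the visit sentence it yields one schedule, day 5, so the fault is loose wording. The outcome list equates the end of washout with five days, and the pre-procedure-2 reading is named as the washout point. The crossover figure is not shown in the copy reviewed and may state the interval. On that reading the early-visit percentages describe departures from the washout sentence. Step outcomes are indexed from each injection, so the windows do not overlap when the injections are 120 hours apart. NRS and OPUS are already taken before procedure 2. The GARS omission would exist whatever the visit window.

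Much of this stands. Day 5 is the probable intent, the percentages are scenarios rather than forecasts, the NRS and OPUS readings at Visit 3 are protected, and GARS is a separate collection gap.

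It does not remove the point. A schedule that can be met at only one instant needs a stated tolerance. A coordinator who books day 3 has followed the Visit 3 section while departing from the washout sentence. The protection of NRS and OPUS does not extend to step counts or to diary entries still due, and on day 5 itself the step window can still cross the second injection.

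**Conclusion.** The concern holds. In the readable text, the Visit 3 timing, the washout and the first-period outcome schedule agree only at exactly day 5, and no data-handling rule applies when they do not. Visits on days 4 to 1, which the Visit 3 sentence allows, would place 1 to 4 of the five daily points after the second injection. On day 5 the residue is 4.2% of the last step window per hour of clock-time difference, plus the missing GARS collection.

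This rests on reading the visit sentence as a latest limit and on a missing figure that cannot be checked. The documents do not say how many participants would attend early, so neither the size nor the direction of any effect on the trial's results can be given.

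The 15-minute primary reading is not overwritten. A shortened washout could reach the second-period primary result only through its baseline or carryover, and the documents give nothing to size that. The sample size of 20 is unaffected. This should be corrected, but it does not undermine the primary analysis.

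**What to change.** 1. Reconcile the Secondary Outcomes, Visit 2, treatment-block and Visit 3 text so that the visit window, the washout and the first-period assessments agree, and state the window with both an earliest and a latest limit. Which interval is right is for the sponsor; none is proposed here.
2. State that the end-of-period-1 NRS, OPUS and GARS are completed, and the period-1 step count is closed, before procedure 2. Add GARS to the Visit 3 list.
3. Add one sentence to the Statistical Plan: no NRS, step or survey value recorded after procedure 2 is attributed to period 1.

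The cost is one wording amendment and one data-handling sentence. The downside is a minor scheduling constraint and, for some participants, a shortened last step window. It should be done before data collection or analysis.

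### OPUS is collected on the day of procedure 2 but not of procedure 1, so change after the first injection is measured from a survey up to 2 weeks old

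*Combined protocol and SAP*

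**What the plan says.** All places are in the combined protocol and SAP.

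- **Visit 1:** "Participants will be asked to complete the OPUS and GARS survey and provide demographic information". The same section says "Participants will provide baseline outcome measures and demographic data".
- **Visit 2 (procedure 1):** "Eligible participants will return to the Lavin 14th floor Pain clinic within 2 weeks of the initial visit". The only score listed before the injection is pain: "Participant pre-procedure 1 NRS pain score will be collected".
- **Visit 3 (procedure 2):** "Participant pre-procedure 2 NRS and OPUS will be collected", followed by "Note that this will serve as post-procedure 1 washout and pre-procedure 2 intervention data point".
- **Telephone calls:** "participant will be called at 1- and 5-days post-procedures for NRS, OPUS survey and safety monitoring by research coordinator".
- **Secondary Outcomes, items 3 and 4:** mean and SD of change in OPUS and in GARS, immediately after injection and at the end of the 5-day washout. The heading adds that "between and within-group comparisons will be used for each outcome".

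No section schedules an OPUS at Visit 2, and none says which earlier score the OPUS change is measured from.

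**The concern.** The Aim covers functional improvement as well as pain relief, and OPUS is one of its measures. NRS is taken on the day of both procedures, but OPUS only on the day of the second. Whatever happens to function between Visit 1 and Visit 2 cannot be due to an injection, yet it is included in the change recorded after the first one.

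Two things are at stake. The planned within-group changes would carry any drift from before the injection. The paired comparison could lose precision, because one of its two changes starts from a staler score. A pre-procedure score that was not collected cannot be recovered at the analysis stage.

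**Working it through.** **1. The plan's own figure.** The Power Analysis gives a discordant difference of 0.625 and a discordant total of 0.875. The two cells are (0.875 + 0.625)/2 = 0.75 and (0.875 − 0.625)/2 = 0.125. Exact two-sided McNemar power at alpha 0.05 is 0.790 with 17 participants and 0.830 with 18. Then 18/(1 − 0.10) = 20, the stated N. It rests on the NRS responder outcome only, so OPUS timing does not touch it.

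**2. Age of the baseline.**

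| | Period 1 | Period 2 |
|---|---|---|
| Last OPUS before injection | Visit 1 | Visit 3 |
| Age at injection | up to 14 days | same day |
| Span of the day-5 change | up to 14 + 5 = 19 days | about 5 days |

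**3. Drift.** Let mean OPUS move by d between Visit 1 and Visit 2, with no injection effect. The period 1 change is d and the period 2 change is 0. With balanced sequences, half of each condition's data come from period 1:

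- lidocaine within-group change = (d + 0)/2 = d/2
- saline within-group change = d/2
- lidocaine minus saline = 0

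A simulation with 18 participants agrees. It assumed, in OPUS SD units, within-person noise SD 0.4 and drift with mean 0.2 and SD 0.3. It gave a false change of 0.10 in each condition and a difference of 0.00. The SE of the difference rose from 0.19 to 0.20, or to 0.22 with drift mean 0.3 and SD 0.5. With an OPUS at Visit 2 the false change was 0.00.

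**4. Variance with period-specific baselines.** The documents give no OPUS SD or reliability, so this is an assumed model: total variance 1, split into stable trait 0.6, slow state 0.3 with day-to-day correlation r, and noise 0.1. Visit 1 is day 0, Visit 2 day 10, Visit 3 day 15.

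*Day-1 call, r = 0.9*
- Period 1 change: 2[0.3(1 − 0.9^11) + 0.1] = 0.61
- Period 2 change: 2[0.3(1 − 0.9) + 0.1] = 0.26
- Their covariance is −0.0135, so the paired difference has variance 0.61 + 0.26 + 0.027 = 0.90
- With a Visit 2 baseline: 0.26 + 0.26 + 0.004 = 0.52, a reduction of 42%
- At r = 0.95: 0.70 falls to 0.46, a reduction of 34%

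*Day 5, with the Visit 3 score as the period 1 outcome and the period 2 baseline, as the plan states.* The paired difference is 2Y15 − Y0 − Y20 with the Visit 1 baseline and 2Y15 − Y10 − Y20 with a Visit 2 baseline (Y is the score, the number is the day).
- Visit 1 baseline, r = 0.9: 0.3(6 − 4×0.9^15 − 4×0.9^5 + 2×0.9^20) + 0.6 = 1.517
- Visit 2 baseline, r = 0.9: 0.3(6 − 8×0.9^5 + 2×0.9^10) + 0.6 = 1.192, a reduction of 21%
- r = 0.95: 1.131 to 0.902, a reduction of 20%
- r = 0.98: 0.830 to 0.721, a reduction of 13%
- r = 0.9 with a 5-day gap between Visits 1 and 2: 1.397 to 1.192, a reduction of 15%
- r = 0.9 with a 1-day gap: 1.242 to 1.192, a reduction of 4%

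**5. Variance with one common baseline B.** (Y1 − B) − (Y2 − B) = Y1 − Y2, where Y1 and Y2 are the two post-injection scores. B drops out, so its age has no effect on the paired contrast. For outcomes 5 days apart at r = 0.9 the variance is 2[0.3(1 − 0.9^5) + 0.1] = 0.45.

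**The case against.** The case for leaving the schedule alone has real force.

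- **The baseline is undefined.** The Visit 1 wording can be read as one common baseline. If so, step 5 applies and nothing is lost in the paired contrast. The Visit 3 wording points the other way, because it names that day's score as the pre-procedure 2 value. Even with a common baseline, the within-group changes would still include the interval before Visit 2.
- **Analysis can do much of the work.** In the assumed model, comparing post-injection scores directly (0.45) beats even same-day change scores (0.52 at day 1, 1.19 at day 5). This stands for the paired contrast. It does not help the within-group changes.
- **The larger variance figure flatters the point.** A reader might infer that the trial wastes 42% of its variance, like needing about 1.7 times the participants (0.90/0.52). That uses the day-1 call, which is not a time point named in item 3, plus an assumed 10-day gap and period-specific baselines. The documents do not support it as a general figure.
- **Drift may be small.** Participants are more than 12 months past amputation with pain for more than 6 months. Entry selects on NRS above 4, not on OPUS, so regression to the mean reaches OPUS only through an unknown correlation. The direction of any drift is also unknown.
- **Within-group changes have no control.** A same-day baseline would remove drift from before the injection, but would not turn them into injection effects.

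The schedule facts are not disputed: the two injections have OPUS baselines of different age, and the protocol gives no reason.

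**Conclusion.** The point holds in a limited form and is of low severity. As written, the first injection's only pre-injection OPUS is up to 14 days old, while the second has a same-day value. The planned within-group changes absorb about half of any mean drift between Visits 1 and 2, in both conditions alike.

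A reader might infer that the lidocaine-minus-saline comparison is biased. The documents do not support that: with 1:1 randomization of sequence the drift cancels in expectation. What remains there is extra variance, and only if each injection's change is taken from its own pre-procedure score. For the Visit 1 to Visit 2 gaps of 5 to 10 days and the correlations tried, a same-day baseline would remove roughly 13–21% of that variance at day 5 and about 34–42% at the day-1 call (10-day gap only). The gain shrinks as the gap closes and is nil under one common baseline. All of these figures rest on assumed parameters.

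A reader might also extend the point to GARS. The asymmetry does not arise there: no GARS is scheduled after Visit 1 at all, which is a different gap.

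The primary NRS outcome and N = 20 are unaffected, and OPUS is an unpowered secondary outcome.

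**What to change.** - **Visit 2:** collect OPUS together with the NRS before procedure 1.
- **Secondary Outcomes, item 3:** define each period's baseline as the same-day pre-procedure OPUS, and say whether the lidocaine–saline comparison uses changes from that baseline or the post-injection scores directly.
- **GARS (item 4):** add it before each procedure only if post-injection GARS collection is also scheduled, as item 4 requires. A Visit 2 GARS alone would not yield that endpoint.

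The OPUS change costs a minor amendment and one more sitting of a short questionnaire at a visit that already takes place, for at most 20 participants. It helps only those who have not yet had procedure 1 when it takes effect.
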